16.2.2. MISSING DATA IMPUTATION METHOD FOR SECONDARY EFFICACY ENDPOINTS

16.2.2.1. Binary Endpoints

For the *incidence of oxygen-free recovery at Day 29* endpoint, the algorithm defined in Section 16.2.1.1 will first be applied. Then, patients with a missing oxygen-free recovery status at Day 29 will be considered as not having met the event for this key secondary efficacy endpoint.

For the *incidence of patients with ≥ 2-point improvement from baseline or fit for discharge on the ordinal scale at Day 29* endpoint (refer to Section 16.2.1.2), patients with a missing ordinal scale score at Day 29 due to patient’s death, discontinuation from study before or on Day 29 or for any other reason (with the following exception) will be considered as not having met the event at Day 29 for that key secondary endpoint. The only exception is for patients with a missing ordinal scale score at Day 29 for which the latest non-missing ordinal scale score before Day 29 was 7 (but not discharge to hospice care) or 8. These patients will be assumed to be fit for discharge at Day 29 and so, as having met the event.

For the *incidence of all-cause mortality through Day 29* endpoint (refer to Section 16.2.1.3), patients with an unknown alive/death status at Day 29 due to discontinuation from study for a reason other than death or missing data will be considered as alive in the analysis, exception of patients for who the last-missing ordinal scale score was 7 and that have been discharged to hospice care before discontinuing from study before Day 29. These patients will be considered as dead at Day 29 for the main analysis of this key secondary efficacy endpoint.

[figure not shown]
For the *clinical recovery by Day 8* endpoint (refer to Section 16.2.1.8), any patient who died before or on Day 8, discontinued from study before or on Day 8 or with missing clinical recovery status at Day 8 will be considered as not having clinical recovery by Day 8. Missing *clinical recovery by Days 15 and 29* will be handled similarly.

For the *sustained clinical recovery as confirmed by Day 60* follow-up endpoint (refer to Section 16.2.1.9), any patient who died before or on Day 60, discontinued study before Day 60 or with a missing 8-point ordinal scale score at Day 60 will be counted as not having sustained clinical recovery.

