Note: Additional assessments, if required, will be defined in the sub-protocol.

a These visits will be performed even if a patient has already been discharged. If discharged prior to scheduled visit, these visits will be conducted via telemedicine. For visits conducted by telephone, it may not be possible to perform some scheduled assessments (eg, vital signs). The Day 29 assessments will also be performed, where possible, for patients who discontinue the study prematurely.

b Medical history includes estimated date and time of first COVID-19 related symptoms and co-morbidities (eg, respiratory [including date of diagnosis of ARDS, if present], cardiovascular, metabolic, malignancy, endocrine, gastrointestinal, immunologic, renal).

- c Oropharyngeal/nasal swab for polymerase chain reaction determination of SARS-CoV-2 or for SARS-CoV-2 antigen testing. Only to be performed if no diagnostic test results are available that have been obtained during the previous 72 hours.
- d If height and/or weight cannot be obtained at the Screening Visit (Day -1 or Day 1), these parameters can be recorded as a combination of patient-reported data and data obtained from recent medical records (ie, at hospital admission).
- e For patients requiring high-flow oxygen, mechanical ventilation (invasive/noninvasive), or extracorporeal membrane oxygenation only, provide FiO2 requirement.
- f Baseline assessments should be performed prior to study drug administration.
- g To be assessed only while hospitalized.
- h Includes oxygen requirement (ie, mode of delivery/liters of oxygen flow, FiO2 requirement), stop date of oxygen for patients who were discharged on home oxygen, extracorporeal membrane oxygenation support, noninvasive or invasive ventilator requirement, including start and stop of low- or high-flow oxygen supply or of any form of ventilation, and need for renal replacement therapy. Noninvasive ventilation refers to the delivery of mechanical ventilation to the lungs using techniques that do not require an endotracheal airway.
- i Only stop date of oxygen for patients who were discharged on home oxygen.
- j Information recorded is yes/no, hospitalization date, discharge date.
- k Laboratory tests performed within the 48 hours prior to enrollment will be accepted for determination of eligibility.

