16.2.2.2. Ordinal Endpoints

Missing *ordinal scale scores* will be imputed as follows for the distribution of patients across the categories of the 8-point ordinal scale for clinical severity at Day 8 endpoints (refer to Section 16.2.1.4):

CCI			
PPD		Version Number:	Amendment 1, v1.0
		Version Date:	23Apr2021
CCI			

- Patients who died prior to Day 8 will have a score of 1 used for Day 8;
- For all other occurrences of patient with missing ordinal score at Day 8 (e.g., patients who discontinued from the study before Day 8, etc.), the last non-missing post-baseline ordinal scale score before Day 8 (included data collected at unscheduled post-baseline visits) will be used to impute the missing ordinal scale score at Day 8 exception of patients for who the last non-missing post-baseline ordinal scale score before Day 8 is 7 that were discharged to hospice care. For these patients, the missing ordinal scale score at Day 8 will be imputed to 1.

Missing ordinal scale score at Days 15 and 29 will be imputed similarly.

For the *worst post-baseline score on the 8-point ordinal scale from baseline to Day 29* endpoint (refer to Section 16.2.1.5), patients who have died prior to Day 29 will have their worst post-baseline ordinal scale score from Day 1 to Day 29 set to a score of 1. For patients who are alive at Day 29, no imputation of missing post-baseline ordinal scale scores will be performed. The worst post-baseline ordinal scale score will be identifying among the non-missing post-baseline ordinal scale scores (including data collected at unscheduled post-baseline visits).

For the *number of ICU days and number of invasive mechanical ventilation days* endpoints (refer to Sections 16.2.1.6 and 16.2.1.7, respectively), missing data will not be imputed.

[figure not shown]

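### The missing-Day-29 exception for the second key secondary endpoint has no readmission check and is unclear on deaths

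*SAP*

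**What the plan says.** The endpoint is defined in Master SAP 16.2.1.2 from the Day 29 ordinal score. Missing scores are handled in 16.2.2.1. The general rule covers scores missing "due to patient’s death, discontinuation from study before or on Day 29". It then adds a residual category and gives the outcome: "or for any other reason (with the following exception) will be considered as not having met the event at Day 29". The exception opens with "The only exception is for patients with a missing ordinal scale score at Day 29 for which the latest non-missing ordinal scale score". It covers a last score of 7, unless the discharge was to hospice, and a last score of 8. Its consequence is explicit: "These patients will be assumed to be fit for discharge at Day 29 and so, as having met the event".

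The exception is judged on the last recorded score and, for a 7, on hospice discharge. It does not refer to the Death Details page or to readmission on the Hospitalization page. Section 16.2.1.2 adds no such check.

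In the Master Protocol schedule (1.3), the ordinal scale is scored daily in hospital and at Days 15, 29 and 60. The separate rehospitalization item for discharged patients carries no score: "Information recorded is yes/no, hospitalization date, discharge date".

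Master SAP 7.4 places this endpoint third in the hierarchy, after the primary endpoint and oxygen-free recovery and before mortality.

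**The concern.** A patient who goes home and then relapses is one whom a Day 29 fit-for-discharge endpoint ought not to count on the strength of the discharge score alone. Take a patient discharged on Day 10 with a 7, admitted elsewhere on Day 20, still an inpatient on Day 29, with no score after the 7. The case report form can hold the admission dates, yet the rule carries the discharge status to Day 29 and records a success.

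Death raises a different problem. The general rule names it as a non-event, but the exception is worded for all patients with a missing Day 29 score. Two programmers could code a post-discharge death differently, on an endpoint that is formally tested. If such cases fell more often in one arm, the error would enter the treatment difference directly.

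**Working it through.** **1. Two test patients under each rule (Master SAP).** Patient A is the readmitted patient above, still in the study. Patient B is discharged with a 7, not to hospice, and dies at home on Day 20 with no score of 1 recorded.

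| Endpoint | Patient A | Patient B |
|---|---|---|
| Primary (16.1.1) | Hospitalization page checked; censored, no event | Death checked first; censored, no event |
| Oxygen-free recovery (16.2.1.1, 16.2.2.1) | Discharge status rests on the missing Day 29 score, so missing, so not met | Dead, so not met |
| Clinical recovery at Day 29 (16.2.2.1) | Missing status, so not recovered | Not recovered |
| Ordinal distribution at Day 29 (16.2.2.2) | Last score, 7, carried forward | Score 1 |
| Improvement or fit for discharge (16.2.2.1) | Met | Unclear |

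The clinical recovery rule fails "any patient who died before or on Day 8, discontinued from study before or on Day 8", and Days 15 and 29 follow the same pattern. The ordinal rule starts with "Patients who died prior to Day 8 will have a score of 1 used for Day 8", again extended to Days 15 and 29. Death is thus explicit in four neighbouring rules. Readmission is checked directly only in the primary endpoint. The ordinal distribution shares the readmission gap, but it is not in the formal hierarchy.

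**2. Does the result for A depend on how the exception is read?** No. A's score is missing for a reason other than death or discontinuation, so the exception applies whether it covers every reason or only the residual one. B's result does depend on it: not met if the parenthesis qualifies only the residual category, met if the exception is taken at its full wording.

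**3. Does the sensitivity analysis correct this?** The multiple imputation in 16.2.4 is for patients who discontinued by Day 29. A did not discontinue, and no rule for known deaths is added.

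**4. The plan's own power figure.** Inputs from Master SAP 7.1 and 7.3: n = 350 per arm, 70% against 79.2%, two-sided 0.05.

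- Mean proportion = (0.70 + 0.792)/2 = 0.746
- SE0 = √(2 × 0.746 × 0.254/350) = 0.0329
- SE1 = √((0.70 × 0.30 + 0.792 × 0.208)/350) = 0.0327
- Power = Φ[(0.092 − 1.96 × SE0)/SE1] = Φ(0.841) = 0.7997

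This reproduces the stated figure of about 80%.

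**5. Illustration of size.** The documents give no rate, so 1% to 3% of an arm is an assumption: 0.01 × 350 = 3.5 to 0.03 × 350 = 10.5 patients. The planned 70% and 79.2% are taken to include these patients, who are then recoded as not met.

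| Recoded, control / active | Difference left (points) | Power |
|---|---|---|
| 1% / 1% | 9.2 | 0.790 |
| 2% / 2% | 9.2 | 0.780 |
| 3% / 3% | 9.2 | 0.771 |
| 0% / 1% | 8.2 | 0.698 |
| 0% / 2% | 7.2 | 0.580 |
| 0% / 3% | 6.2 | 0.456 |

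With no true effect (70% in both arms) and a spurious excess d in the active arm, the chance of a result favouring the agent is 1 − Φ[(1.96 × SE0 − d)/SE1]. For d = 0.01 this is 1 − Φ(1.67) = 0.047; for 0.02 it is 0.084; for 0.03 it is 0.140, against a nominal 0.025. These figures are for the test taken alone, ignoring the two gates before it.

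**The case against.** A reader might infer that the SAP plainly counts post-discharge deaths as successes. The text does not support that. Death comes first in the list of non-events, and the parenthesis directly follows the residual category, so it can be read as qualifying that category alone. Death is also category 1 of the scale: if a 1 was entered on or before Day 29, the last score is no longer 7 or 8. What stands is that the wording admits both readings.

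A reader might also infer that every patient last scored 7 or 8 is covered. A 7 discharged to hospice is expressly excluded.

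The readmission case is narrow. It needs an admission lasting through Day 29, no ordinal score recorded during it, a missed Day 29 assessment, and dates that still reach the case report form. Daily scoring in hospital would normally replace the 7 or 8. The gap remains because the rule relies on a score being entered and does not consult the page that holds the admission dates. Nor does being in hospital prove failure: category 6 is an inpatient category, and a patient with a baseline of 2 or 3 could have gained two points. But without a score neither is shown, and the plan's default for a missing score is not met.

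Finally, one might infer that an agent which speeds discharge but increases relapse would be rewarded. It would first have to win on the primary endpoint, which gives no event for death or readmission after a 7 or 8, and on oxygen-free recovery, which fails the dead and those with missing status. Mortality is tested next. This limits the practical harm considerably.

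**Conclusion.** The exception misclassifies a discharged patient known to be back in hospital on Day 29 with no later score, and this holds on either reading. For deaths the defect is ambiguity, not a clear rule that counts them as successes.

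The size cannot be derived from the documents and is probably small. Equal misclassification leaves the 9.2-point difference unchanged and costs 1 to 3 points of power under the assumed 1% to 3%. The larger effects calculated above require an excess in one arm, which the documents give no reason to expect. The reach is also limited: the COV-01-001 and COV-01-005 SAPs (section 16 of each) make no efficacy inference, so there only descriptive tables are affected. The COV-01-004 SAP takes its efficacy analyses from the Master SAP, so its third formal test is the one exposed.

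**What to change.** In Master SAP 16.2.2.1, before the exception, state that a patient is not met if there is a Death Details record on or before Day 29, or a Hospitalization record that starts after the 7 or 8 score and is still open on Day 29. Then apply the exception only to the remaining patients with a missing Day 29 score.

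The cost is one sentence and one programming check. Both case report form pages are already read for the primary endpoint, so no new data are needed. The change should be made before the database lock for the COV-01-004 primary analysis.

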
 
To evaluate invasive mechanical ventilator days
 
	
 
Number of invasive mechanical ventilator days from Day 1 through Day 29.
 

 
To evaluate clinical recovery
 
	
 
Incidence of clinical recovery, as defined by achieving a score of 6, 7, or 8 on the 8-point ordinal scale of clinical severity status by Days 8, 15, and 29.
 

 
To evaluate sustained clinical recovery
 
	
 
Incidence of sustained clinical recovery as confirmed by Day 60 follow-up.
 

 
To evaluate the safety of candidate agents as add-on therapy to standard of care (SoC) in patients with COVID-19
 
	
 
Incidence of adverse events (AEs) in the following categories:                             
 
All treatment-emergent AEs
 
Serious AEs
 
AEs with Common Terminology Criteria for Adverse Events Grade 3 or higher
 
AEs leading to dose modifications
 
AEs leading to study treatment discontinuation
 
 
 

Exploratory	

CCI
	

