
 
To evaluate intensive care unit (ICU) days
 
	
 
Number of ICU days from Day 1 through Day 29.
 

 
To evaluate invasive mechanical ventilator days
 
	
 
Number of invasive mechanical ventilator days from Day 1 through Day 29.
 

 
To evaluate clinical recovery
 
	
 
Incidence of clinical recovery, as defined by achieving a score of 6, 7, or 8 on the 8-point ordinal scale of clinical severity status by Days 8, 15, and 29.
 

 
To evaluate sustained clinical recovery
 
	
 
Incidence of sustained clinical recovery as confirmed by Day 60 follow-up.
 

 
To evaluate the safety of candidate agents as add-on therapy to standard of care in patients with COVID-19
 
	
 
Incidence of AEs in the following categories:                         
 
All treatment-emergent AEs
 
Serious AEs
 
AEs with Common Terminology Criteria for Adverse Events Grade 3 or higher
 
AEs leading to dose modifications
 
AEs leading to study treatment discontinuation
 
 
 

Exploratory
	

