**Table 2 Clarification of the 8-point Ordinal Scale for Scores 2 Through 5**

Ordinal Scale Score	General Description	Expanded Description
2	IMV or ECMO	ECMO or IMV, which includes closed systems, utilizing endotracheal intubation or tracheostomy, with ventilator assistance.
3	NIV, high-flow oxygen delivery ( $\geq 10$ L/min)	NIV includes APAP, BiPAP, and CPAP. High-flow delivery systems include HFNC, non-rebreather face mask, and venturi mask where the oxygen flow rate is $\geq 10$ L/min.
4	Low-flow oxygen delivery ( $< 10$ L/min)	Low-flow oxygen delivery systems include simple face mask and simple nasal cannula where the oxygen flow rate is $< 10$ L/min.
5	No oxygen requirement	Not requiring supplemental oxygen but requiring in-hospital medical care for any active medical issues.

Abbreviations: APAP = automatic positive airway pressure; BiPAP = bilevel positive airway pressure; CPAP = continuous positive airway pressure; ECMO = extracorporeal membrane oxygenation; HFNC = high-flow nasal cannula; IMV = invasive mechanical ventilation; min = minute; NIV = noninvasive ventilation.

A patient will be considered as fit-for-discharge if he/she achieves a score of 6, 7, or 8 on the ordinal scale (ie, as a minimum, the patient does not require ongoing hospitalized medical care) at least once on the study. Patients who achieve a 7 on the ordinal scale but are discharged to hospice care will not be considered as being fit-for-discharge.

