Refer to Section 16.2.2.2 for handling of missing number of ICU days from Day 1 through Day 29.

16.2.1.7. Number of Invasive Mechanical Ventilator Days from Day 1 through Day 29

For each patient, the ‘other secondary efficacy endpoint’ of the number of invasive mechanical ventilator days from Day 1 through Day 29, inclusively, will be considered as an ordinal endpoint and derived similarly to the number of ICU days from Day 1 through Day 29 (refer to Section 16.2.1.6) but using the data collected on the *Supplemental Oxygen and Mechanical Ventilation* page of the eCRF where *Type of supplemental oxygen* is recorded as *Invasive Mechanical Ventilation*.

Refer to Section 16.2.2.2 for handling of missing number of invasive mechanical ventilation days from Day 1 through Day 29.

16.2.1.8. Incidence of Patients with Clinical Recovery by Days 8, 15, and 29

[figure not shown]
An ‘other secondary efficacy endpoint’ is the incidence of patients with clinical recovery at Days 8, 15, and 29, defined as the proportion of patients being fit for discharge (i.e., patients achieving a score of 6, 7, or 8 on the 8-point ordinal scale for clinical severity; refer to Section 16.1.1) at Days 8, 15, and 29, respectively, as per data recorded on the *Ordinal Scale for Clinical Severity* page of the eCRF. It is to be noted that patients with a score of 7 discharged to hospice care will not be considered as being fit for discharge for this ‘other secondary efficacy endpoint’.

Refer to Section 16.2.2.1 for handling of missing clinical recovery status by Days 8, 15, and 29.

16.2.1.9. Incidence of Patients with Sustained Clinical Recovery as Confirmed by Day 60 Follow-up

An ‘other secondary efficacy endpoint’ is the incidence of patients with sustained clinical recovery as confirmed by Day 60 follow-up, defined as the proportion of patients considered as being fit for discharge (i.e., achieving a score of 6, 7, or 8 on the 8-point ordinal scale for clinical severity) through Day 29, without re-hospitalization by Day 60 (refer to Section 16.1.1), as per the *Ordinal Scale for Clinical Severity* and *Hospitalization* pages of the eCRF. It is to be noted that patients with a score of 7 discharged to hospice care before or on Day 29 will not be considered as being fit for discharge for this ‘other secondary efficacy endpoint’.

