16.2.3.1. Binary Endpoints

For the incidence of patients with oxygen-free recovery at Day 29 (refer to Section 16.2.1.1), incidence of patients with ≥ 2 -point improvement from baseline or fit for discharge on the ordinal scale at Day 29 (refer to Section 16.2.1.2), incidence of all-cause mortality through Day 29 (refer to Section 16.2.1.3), incidence of patients with clinical recovery at Days 8, 15 and 29 (refer to Section 16.2.1.8), and incidence of patients with sustained clinical recovery as confirmed by Day 60 follow-up (refer to Section 16.2.1.9), the number and percentage of patients with and without the event will be provided by treatment arm. For the incidence of all-cause mortality, primary reason of death will also be summarized by treatment arm.

For each of these endpoints, a logistic regression will be performed to test the difference between a candidate agent plus SoC and placebo plus SoC treatment arms, including the baseline clinical severity of 2 on the 8-point ordinal

scale for clinical severity (yes or no) stratification variable, remdesivir use at baseline (yes or no) stratification variable, both as captured on the IWRS, country (region; refer to Section 7.5), and treatment arm as factors. The estimate of the relative risk (risk difference) between the two treatment arms, the corresponding two-sided 95% Wald CI, and the p-value obtained from the logistic regression model will be provided.

The odds ratio (of candidate agent plus SoC vs. placebo plus SoC) for having the event at the specified Day and its two-sided 95% CI will also be presented.

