16. EFFICACY ENDPOINTS

[figure not shown]
Efficacy analyses are described in the Master COV-01 SAP.

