16.2.3.1. Binary Endpoints

For the incidence of patients with oxygen-free recovery at Day 29 (refer to Master SAP Section 16.2.1.1), incidence of patients with ≥ 2 -point improvement from baseline or fit for discharge on the ordinal scale at Day 29 (refer to Master SAP Section 16.2.1.2), incidence of all-cause mortality through Day 29 (refer to Master SAP Section 16.2.1.3), incidence of patients with clinical recovery at Days 8, 15 and 29 (refer to Master SAP Section 16.2.1.8), and incidence of patients with sustained clinical recovery as confirmed by Day 60 follow-up (refer to Master SAP Section 16.2.1.9), the number and percentage of patients with and without the event will be provided by treatment arm. Two-sided 95% exact binomial CI will also be provided by treatment arm for the percentage of patients with the event.

For the incidence of all-cause mortality, primary reason of death will also be summarized by treatment arm.

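### Clinical recovery is defined both 'at' and 'by' Day 8; if programmed as 'at', the SAP's missing-data rule counts patients already discharged as not recovered

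*SAP*

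**What the plan says.** **Texts that say *by*.** The protocol synopsis and Protocol Table 1 define this other secondary endpoint as "achieving a score of 6, 7, or 8 on the 8-point ordinal scale of clinical severity status by Days 8, 15, and 29". The heading and closing line of Master SAP 16.2.1.8, and the name given to the endpoint in 16.2.2.1, also say *by*. Protocol 8.1.1 treats a patient as fit for discharge once a score of 6, 7 or 8 is reached, that is, when "the patient does not require ongoing hospitalized medical care) at least once on the study".

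**Texts that say *at* or *on*.** The defining sentence of Master SAP 16.2.1.8 gives the "incidence of patients with clinical recovery at Days 8, 15, and 29, defined as the proportion of patients being fit for discharge" on each of those days, taken from the Ordinal Scale page of the eCRF. Master SAP 16.2.3.1 and section 16.2.3.1 of the COV-01-001 SAP analyse or summarise "clinical recovery at Days 8, 15 and 29 (refer to Section 16.2.1.8"). The COV-01-005 SAP has "clinical recovery at Days 8, 15 and 29 (refer to Master SAP Section 16.2.1.8"). A later sentence of Protocol 8.1.1 says *on*. For COV-01-004 (apremilast) the SAP states only that "Efficacy analyses are described in the Master COV-01 SAP".

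**Missing data.** Under Master SAP 16.2.2.1, any patient who died or discontinued on or before Day 8, or "with missing clinical recovery status at Day 8 will be considered as not having clinical recovery by Day 8". Days 15 and 29 are handled in the same way. There is no exception for patients already discharged.

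**Schedule.** In Protocol 1.3 the ordinal scale is scored at baseline, daily until discharge, and then at Days 15, 29 and 60. Protocol 4.1 gives patients discharged before Day 15 outpatient visits at Days 15 and 29.

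**The concern.** *At Day 8* and *by Day 8* are different endpoints. The first is status on one day; the second is whether the score was ever reached up to that day. Two programmers could build different variables and each cite the plan. Master SAP 3.3 lists no change to this endpoint, so the *at* wording does not look like a deliberate departure from the protocol.

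The difference matters at Day 8 because of the visit schedule. A patient sent home on Day 5 has a score up to discharge and then nothing planned until Day 15. On the *at* definition that patient has no Day 8 score to classify, and the missing-data rule supplies the answer: not recovered. The fastest recoverers would then be counted as failures.

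The same SAP treats the same gap differently for the Day 8 ordinal distribution. There, section 16.2.2.2 carries the last post-baseline score forward, so a patient last scored 7 (not hospice) or 8 appears in that category at Day 8.

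**Working it through.** **Step 1. Follow one patient through both readings.** Take a patient scored 8 at discharge on Day 5, alive and in the study at Day 8.

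| Output | Rule | Day 8 result |
|---|---|---|
| Clinical recovery, *by* reading | Protocol Table 1 | Recovered |
| Clinical recovery, *at* reading | Master SAP 16.2.1.8 with 16.2.2.1 | No Day 8 score, so not recovered |
| Day 8 ordinal distribution | Master SAP 16.2.2.2 | Category 8 |

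The *by* result relies on a 6, 7 or 8 having been recorded up to the day of discharge, which daily scoring until discharge should provide.

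**Step 2. Can windowing supply a Day 8 score?** Master SAP 6.4 maps discharge data to scheduled visits using an adjusted protocol window, but does not say what the adjustment is. The ordinal-scale schedule gives windows only for Day 15 (±2), Day 29 (±3) and Day 60 (±4). Section 6.3 keeps unscheduled visits out of by-visit summaries. At most, a discharge very close to Day 8 might be rescued.

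**Step 3. Illustrate the size.** The plan gives no rate or power for this endpoint, so there is no stated figure to reproduce.

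Inputs:
- Medians of 15 days (placebo) and 11 days (active), and 350 patients per arm, from Protocol 9.1 and Master SAP 7.1. The medians are for confirmed recovery and stand in here for simple recovery.
- Exponential times. This matches the plan's hazard ratio: 15/11 = 1.364.
- *f*, the share of patients recovered by Day 7 who are already home at Day 8. The documents do not give it. It is varied and assumed equal in both arms.

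Proportion recovered by day *t* with median *m*: F(t) = 1 − 2^(−t/m).
- Placebo: F(7) = 1 − 2^(−7/15) = 0.27637; F(8) = 1 − 2^(−8/15) = 0.30904.
- Active: F(7) = 1 − 2^(−7/11) = 0.35667; F(8) = 1 − 2^(−8/11) = 0.39596.

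Rate reported on the *at* reading = F(8) − f × F(7). Patients miscounted per arm = 350 × f × F(7).

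| f | Placebo | Active | Difference (points) | Miscounted, placebo / active |
|---|---|---|---|---|
| 0 (no miscount) | 30.9% | 39.6% | 8.7 | 0 / 0 |
| 0.25 | 24.0% | 30.7% | 6.7 | 24 / 31 |
| 0.50 | 17.1% | 21.8% | 4.7 | 48 / 62 |
| 0.75 | 10.2% | 12.8% | 2.7 | 73 / 94 |

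For example, at f = 0.75 in the active arm: 0.39596 − 0.75 × 0.35667 = 0.12846, or 12.8%.

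The model is rough. It ignores death and discontinuation, and by Day 29 it would give 350 × (0.7382 + 0.8392) = 552 recoveries against the plan's 490.

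**Step 4. Days 15 and 29.** Both have scheduled scores for discharged patients, so the missing-data rule affects them only when a visit is missed.

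**The case against.** The strongest reply is that the plan does not compel the miscount. *By* is the wording of the protocol endpoint, of the heading and closing line of Master SAP 16.2.1.8, and of the endpoint name in the missing-data rule. That rule also speaks of a missing recovery *status*, whereas for key secondary endpoint 2 and sustained recovery the same section speaks of a missing ordinal scale *score*. Since Protocol 8.1.1 counts a patient as fit for discharge once the score is reached at least once, a patient discharged on Day 5 arguably has a known status. This stands: the text is ambiguous, and a careful programmer could reach the right answer. It does not remove the point, because the sentence that defines the endpoint and the sentence that analyses it both say *at*.

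Two further replies also stand. The binary and ordinal tables can differ by design, because discontinued patients are carried forward in one and counted as not recovered in the other; only the disagreement over discharged patients is at issue. And the consequence is small. Master SAP 7.4 gives non-key secondary endpoints nominal p-values only. COV-01-001 (about 34 patients expected) and COV-01-005 (less than a third of about 700) report this endpoint descriptively. Early recovery is also captured by the primary time-to-event analysis and the Day 8 ordinal distribution, neither of which has this gap.

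**Conclusion.** The point holds as a conditional one. If Master SAP 16.2.1.8 is programmed as written, patients discharged before Day 8 are classed as not recovered and both arms' Day 8 rates are understated. If *by* is programmed, there is no miscount. How far the rates fall depends on the share already home, which the documents do not give; Step 3 shows a range, not a prediction.

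A reader might infer more, and the documents do not support it:
- **A bias of known direction in the treatment difference.** The difference shrinks in the table only because the share home was set equal in both arms. With unequal shares it could move either way, and nothing in the documents indicates the shares.
- **An effect on the primary endpoint or type I error.** The primary endpoint uses its own event and censoring algorithm, and this endpoint is outside the testing hierarchy.
- **A similar fault in key secondary endpoint 2.** Section 16.2.2.1 has an exception for patients whose last score was 7 (not hospice) or 8. It could be read to cover someone who later died or was readmitted with no later score. But the general rule names death as not met, and readmitted patients are scored daily in hospital. A clarifying sentence is optional and is not part of this point.

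**What to change.** In Master SAP 16.2.1.8, 16.2.2.1 and 16.2.3.1, define clinical recovery by Day X as a score of 6, 7 (not discharged to hospice) or 8 recorded on or before Day X, in line with the protocol tables. Apply the missing-means-not-recovered rule only when no such score was recorded by Day X. Keep the existing rules for death and discontinuation on or before Day X.

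The sub-protocol SAPs refer to the Master SAP definition, so they need only *at* changed to *by* in section 16.2.3.1 of the COV-01-001 and COV-01-005 SAPs. The COV-01-004 SAP follows the Master SAP without change.

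The cost is a wording alignment and minor programming. No new data are needed: the Ordinal Scale, Hospitalization, Death Details and Disposition pages already hold what the rule uses.
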